## 4.0 Study Endpoints (if applicable)

### Primary Outcome:

The primary outcome measure will be HADS, which is a conventional, validated, and widely used measure of psychosocial functioning. This scale consists of 14 items, seven of which contribute to a depression scale and seven that contribute to an anxiety scale. Therefore, three scores can be derived from this measure: an overall score, depression score, and anxiety score. The overall score will be used as the primary outcome measure and this measure will be administered at baseline, at each weekly psychosocial intervention session, post-treatment, and at 1-month follow up.

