### Secondary Outcomes:

Secondary measures of psychosocial functioning that are specifically validated for the aphasia population will be administered as well, including the D-VAMS, SASS, Stroke Aphasia Depression Questionnaire-10 (SADQ-10; Sutcliffe & Lincoln, 1998), Behavioural Outcomes of Anxiety Scale (BOA; Kneebone et al., 2012; Linley-Adams et al., 2014, Modified Perceived Stress Scale (mPSS; Hunting Pompon et al., 2018), Stroke Aphasia Quality of Life (SAQOL-39; Hilari et al., 2003), and Communication Confidence Rating Scale for Aphasia (CCRSA; Cherney et al., 2011; Babbitt et al., 2011). Most of these will be administered at baseline, post-treatment, and at 1-month follow-up (see below for a table with the timepoints for each measure and the rationale for inclusion). Two of these outcome measures will be also administered at the weekly sessions, including the D-VAMS and SASS.

A questionnaire related to attendance, retention and adherence to outpatient speech therapy services will also be collected at post-treatment to gather preliminary data on whether the psychosocial intervention was associated with good retention/in/adherence to rehabilitation activities. This will be done by administering a questionnaire to participants asking questions about whether they are receiving rehabilitation therapy, and if so, whether they have been attending and following recommendations.

Qualitative interviews will also be conducted at post-treatment and 1-month follow-up to aid in intervention refinement as well. Care partners of participants (e.g., family, friends, spouse) will be invited to participate in the interviews as well.

Table 1. Study Measures

Test Name	Construct	Timepoints	Justification
Primary			
Hospital Anxiety and Depression Scale (HADS)	Measures presence of signs/symptoms of depression and anxiety	All sessions	Overall assessment of psychosocial functioning
Secondary			
Dynamic Visual Analog Mood Scale (D-VAMS)	Measures mood based on reported feelings for 7 scales of emotion	All sessions	A weekly measure of mood fluctuations throughout the study
Simple Aphasia Stress Scale (SASS)	Measures perception of current stress level	All sessions	A weekly measure of acute stress

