## 12.0 Data Management

With 10 participants with aphasia, we are statistically powered to conduct feasibility analyses. For our primary quantitative analysis, we plan to conduct paired-samples *t*-tests to compare each outcome measure with 2 time points: baseline vs. post-treatment and baseline vs. 1-month follow-up. Baseline vs. post-treatment comparisons will be used to examine preliminary effects of the intervention on our primary outcome measures (HADS depression scores, HADS anxiety scores), and the secondary outcome measures listed above. Baseline vs. 1-month follow-up comparisons will be used to examine any delayed or maintained treatment effects on the primary and secondary outcome measures. Quantitative feasibility data and psychosocial data will also be examined descriptively given the small sample size.

Data gathered from the retention/adherence to speech therapy questionnaire and the semi-structured interview will also be analyzed descriptively and qualitatively for emergent themes that can be used to further refine and develop the psychosocial intervention.

To maintain participant confidentiality, all participants will be given a participant study ID which will be used on all their study documents and data. Participant names and direct identifiers will be stored separately from collected data and participant names and study IDs will be linked in one password-protected document saved on an MUSC Network computer or cloud-based storage account. Data will be stored in a secure data capture platform, on an MUSC Network computer or cloud-based storage account, and/or on paper in a locked file cabinet in a locked room on campus to which only research personnel have access. Interviews will be audio recorded and transcribed

for analysis. Audio recordings will be made on a Sony digital recorder and transferred as soon as possible after the session to an MUSC Network computer or a cloud-based storage account to which only research personnel have access. Once transferred, audio recordings will be deleted off the recording device. Consent forms will be stored separately from the data collected in a locked file cabinet in a locked room to which only relevant study personnel have access.

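### Section 12.0 makes paired t-tests of every outcome at two time contrasts the primary quantitative analysis, with no lead test, and its primary HADS scores differ from Section 4.0

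*Combined protocol and SAP*

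**What the plan says.** Section 12.0 (Data Management) sets out paired-samples t-tests "to compare each outcome measure with 2 time points", namely baseline against post-treatment and baseline against 1-month follow-up. All of these tests together carry the label of primary quantitative analysis. The same paragraph applies the baseline to post-treatment comparison to the "primary outcome measures (HADS depression scores, HADS anxiety scores), and the secondary outcome measures listed above", and uses the baseline to 1-month comparison to look for delayed or maintained effects on the same outcomes. It describes the post-treatment effects as preliminary and adds that the data will be examined descriptively as well, because the sample is small. It gives no significance level, no sidedness, no multiplicity rule and no ordering of the tests.

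Section 4.0 (Study Endpoints) notes that "three scores can be derived from this measure: an overall score, depression score, and anxiety score" and then chooses one of them: "The overall score will be used as the primary outcome measure". It lists when the HADS is administered (baseline, weekly sessions, post-treatment, 1-month follow-up) but does not say which time contrast is primary. It names seven secondary instruments: D-VAMS, SASS, SADQ-10, BOA, mPSS, SAQOL-39 and CCRSA. Table 1 describes the D-VAMS as follows: "Measures mood based on reported feelings for 7 scales of emotion".

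**The concern.** Two things go wrong together. First, the outcome that Section 4.0 declares primary is not the one that Section 12.0 analyses as primary. Section 12.0 names the two subscale scores. The overall score is covered, if at all, only by the general reference to each outcome measure. Second, no test is singled out, so all outcomes and both contrasts stand on the same footing. An analyst could lead the report with any of three HADS scores at either of two time points, or with any secondary scale, after seeing the data.

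What is at stake is how the pilot is read afterwards. Section 1.0 states directional efficacy hypotheses (less psychosocial impairment, better quality of life). With 10 completers and many unranked p-values, one nominally significant change could be taken as an efficacy signal for the next study although it is compatible with chance.

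**Working it through.** **Inputs from the documents.** HADS scores: 1 (overall, Section 4.0), 2 (subscales, Section 12.0) or 3 (all that can be derived). Secondary instruments: 7 (Section 4.0). Contrasts: 2 (Section 12.0). Completers: 10 (Sections 6.0 and 12.0). The plan states no error rate, so there is no figure of its own to reproduce.

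**Assumptions, not in the documents.** Two-sided 5% level per test, no adjustment, no true mean change on any outcome. Correlation between change scores on different outcomes from 0 to 0.7. Correlation between the two contrasts 0.5 in the correlated cases.

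**Number of tests** = scores × 2 contrasts.
- HADS overall only: (1 + 7) × 2 = 16
- Two subscales: (2 + 7) × 2 = 18
- All three HADS scores: (3 + 7) × 2 = 20
- All three HADS scores, with D-VAMS split into seven scales: (3 + 6 + 7) × 2 = 32

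**Expected false positives** = m × 0.05, whatever the correlation: 0.8 (16), 0.9 (18), 1.0 (20), 1.6 (32). Counting only apparent benefit, m × 0.025 gives 0.4 to 0.5 for 16 to 20 tests.

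**Chance of at least one, independent tests.**
- Either direction, 1 − 0.95^m: 56.0% (16), 60.3% (18), 64.2% (20), 80.6% (32).
- Apparent benefit only, 1 − 0.975^m: 33.3%, 36.6%, 39.7%, 55.5%.

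**Chance of at least one, correlated tests.** Simulated paired t-tests with n = 10, equal correlation r between outcomes, contrast correlation 0.5:

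| Tests | Either direction: r = 0.5 | r = 0.7 | Benefit only: r = 0.5 | r = 0.7 |
|---|---|---|---|---|
| 16 | 44% | 35% | 23% | 18% |
| 18 | 47% | 37% | 24% | 19% |
| 20 | 49% | 38% | 26% | 20% |
| 32 | 61% | 47% | 33% | 24% |

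Two sensitivity checks change little. Raising the contrast correlation to 0.7 lowers the 16-test figures at r = 0.7 to about 32% and 16%. Treating HADS overall as the sum of its two subscales, as it is by construction, gives about 47% instead of 49% for 20 tests at r = 0.5.

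**For comparison**, a single score at a single contrast has a 5% chance of a false positive in either direction, and 2.5% in the direction of benefit.

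**The case against.** The strongest reply is that this is a pilot. Section 1.0 makes feasibility and acceptability the main objective, Section 6.0 chooses the sample on feasibility grounds, and Section 12.0 calls the effects preliminary and adds descriptive examination. No success criterion or go/no-go rule depends on any of the t-tests. All of this stands and limits how serious the point is. It does not remove the point: the descriptive work comes in addition to the tests, the tests still hold the primary label, and the disagreement over the primary HADS score remains whatever the purpose of the study.

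Stronger readings are tempting, and the documents do not support them.

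- A reader might infer that a spurious effect is more likely than not under most assumptions. For 16 to 20 tests that needs low to moderate correlation between outcomes; at a correlation of 0.5 the figure is already below 50%. Independence is an upper bound here: both contrasts subtract the same baseline, the HADS overall score contains its subscales, and Table 1 includes SADQ-10 and BOA for comparison with the HADS. If a spurious effect means apparent benefit, the direction hypothesised, 16 to 20 tests never exceed 40%.
- A reader might infer that Section 12.0 commits the study to 32 tests. Table 1 lists the D-VAMS as one measure, and nothing says that its seven scales are tested separately. What the documents support is that its score for analysis is unspecified.
- A reader might infer that Section 4.0 already fixes the lead comparison. It fixes the score only.

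**Conclusion.** The concern holds in a limited form. As written, Section 12.0 spreads the primary label over 16 to 20 paired t-tests with no error control and leaves the outcome that Section 4.0 declares primary without a lead analysis. If nothing works, the chance of at least one nominally significant result is about 35% to 64%, or about 18% to 40% for apparent benefit, against 5% and 2.5% for one named test. These figures rest on the assumed 5% level and on the assumed correlations. Only the test counts come from the documents, and the expected 0.8 to 1.0 false positives need the 5% level but no correlation. Because the study is a pilot and nothing is decided on these tests, the point is of moderate weight: it should be corrected, but it does not undermine the design.

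**What to change.** In Section 12.0:

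1. Name one lead efficacy contrast: the HADS overall score, baseline versus post-treatment (Session 6). The score then agrees with Section 4.0; the contrast has to be added because Section 4.0 does not give one.
2. Report the HADS subscales, all secondary outcomes and the baseline to 1-month contrast as mean change with a 95% confidence interval and individual values, with no significance claim.
3. Prespecify the one D-VAMS score that will be analysed.

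This changes wording only; no visit, participant or measurement is affected. The downside is fewer nominally significant secondary results to report. A formal multiplicity adjustment of the secondary outcomes is not requested. With n = 10 and an assumed standardised change of 0.8, power at the first Holm step over 14 secondary tests (7 × 2) would be about 17%, against 62% unadjusted, and estimates with intervals serve a pilot better.

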## **15.0 Risks to Subjects**

There is minimal risk to participants in this study. Participants with aphasia may experience occasional frustration during administration of the assessments if they are not performing as well as they like. If this occurs, breaks and emotional support will be provided by the research team. In addition, due to the emotional nature of some assessments and of the psychosocial intervention, participants may experience some negative emotions/psychological discomfort during discussions about adapting to life after a stroke. If this occurs, emotional support will be provided by the research teams and participants will be given a break, if needed. If participants demonstrate or reveal any concerns that would require more urgent mental health support, such as expressing thoughts of suicide, violence, or substance abuse, they will be referred to a mental health expert immediately. We have included a list of mental health referrals in the application in the General Comments 2.0 section of the IRB application. This list will be used to identify an appropriate provider, and the contact information will be provided to the participant. If a participant is demonstrating signs of a mental health emergency determined in consultation with the Co-Investigator and clinical psychologist, [name], then the participant will be taken to the Emergency Room or 911 will be called. In addition, if participants would benefit from ongoing mental health support/counseling after completion of the study then they will be given the list of mental health providers to choose from. Finally, though efforts will be made to maintain confidentiality, there is a small risk of a confidentiality breach of participant data (for participants with aphasia and care partner interview data). Participants will be warned of these risks during the consent process prior to their agreeing to partake in the research study.

## **16.0 Potential Benefits to Subjects or Others**

Participants with aphasia may benefit from the psychological intervention in terms of their psychological well-being, however, this is not guaranteed as this is an experimental intervention. Although it may or may not benefit participants directly, the information we gather from this study could help us better address the psychological need of people with aphasia in the future as well. Care partners of participants with aphasia will not directly benefit from their participation in the

interviews, but their perspectives could help us refine and develop the intervention to help future patients with aphasia.

## 17.0 Sharing of Results with Subjects

Participants may request copies of their assessments for their own use or to provide to their primary care physicians or a mental health professional. Informal verbal request is all that will be required to obtain documents. All assessments are coded and labeled with a participant number. At the end of the study, participants will be provided with additional mental health resources and contact information for additional mental health services if, according to their assessments, they continue to have symptoms of depression, anxiety, or other psychosocial needs.

